3. OBJECTIVES, OUTCOME MEASURES, AND ENDPOINTS

3.1. Primary Objective/Endpoint

The primary objective of this study is:

- To evaluate the effect of quizartinib on the PK of dabigatran.

The primary endpoint of this study is:

- Single dose PK parameters of dabigatran (measured as total and free dabigatran) with and without concomitant administration of quizartinib, to include: Cmax, AUClast, and AUCinf.

3.2. Secondary Objectives/Endpoints

The secondary objectives of this study are:

- To evaluate the PK profile of dabigatran (measured as total and free dabigatran) administered alone and concomitantly with quizartinib.
- To evaluate the PK profile of single dose quizartinib administered in the presence of dabigatran etexilate.
- To evaluate the PK profile of the metabolite AC886 after single dose administration of quizartinib in the presence of dabigatran etexilate.
- To evaluate the safety and tolerability of quizartinib administered in the presence of dabigatran etexilate.

The secondary endpoints of this study are:

- Single dose PK parameters of dabigatran in Period 1 (administered alone) and Period 2 (administered with quizartinib), to include: Tmax, t_{1/2}.
- Single dose PK parameters of quizartinib, including but not limited to, Cmax, Tmax, and AUClast,₇₄, as applicable.
- Single dose PK parameters of AC886, including but not limited to, Cmax, Tmax, and AUClast,₇₄, as applicable.
- Occurrence of treatment-emergent adverse events (TEAEs); clinically significant changes in laboratory assessments, triplicate 12-lead ECG evaluations, and vital signs.

3.3. Rationale for Selection of Primary and Key Secondary Endpoints

The objectives and endpoints selected for this study are consistent with those used for determination of drug-drug interaction (DDI) studies.

4. STUDY DESIGN

4.1. Overall Design

This is a Phase 1, open-label, 2-period, fixed-sequence, DDI study in healthy male and female subjects designed to evaluate the effect of a single oral dose of 60 mg quizartinib on the PK of a single oral dose of 150 mg dabigatran etexilate. The subject population is described in Section 5. A flow diagram of study activities is presented in [Figure 1.1](#).

4.1.1. Design Overview

A maximum of 20 eligible healthy subjects will be enrolled. There will be 2 treatment periods: all subjects will receive dabigatran etexilate in Period 1 (Reference Treatment) and quizartinib 2 hours prior to dabigatran etexilate administration in Period 2 (Test Treatment).

Following a Screening Period of up to 21 days where subject eligibility will be confirmed, subjects will be admitted to the clinical research unit (CRU) on the day prior to dosing (Day -1) and remained domiciled in the CRU for the duration of the study. At CRU admission, eligibility will be reconfirmed and baseline safety evaluations, including ECGs recorded in triplicate will be assessed.

4.1.2. End-of-Study

Subjects will be discharged from the CRU and from the study at end of study (EOS) on Day 12 after study procedures are completed. Subjects may be discharged from the CRU post Day 7 of quizartinib dosing if safety parameters are acceptable to the investigator. Completion of all planned assessments through CRU discharge will be considered the EOS. Study visits and assessment timing are outlined in [Table 1.1](#).

4.1.3. Dose Regimen

On the morning of Day 1 of Period 1, a single dose of 150 mg dabigatran etexilate will be orally administered as one 150 mg capsule to subjects in the fasted state (after at least 10 hours fast) with approximately 240 mL of water. Subjects will continue to fast for at least 4 hours after dosing. Water should be restricted 1 hour before and 1 hour after dosing and allowed ad libitum outside of this window. Serial blood samples for PK analysis will be taken at: predose, and 0.5, 1, 1.5, 2, 3, 4, 6, 8, 12, 24, 36, 48, 60, and 72 hours post-dabigatran etexilate dose. Safety evaluations (adverse events [AEs], clinical labs, concomitant medication, triplicate ECGs, and vital signs) will be collected through 72 hours after dosing. Safety assessments occurring from the administration of dabigatran etexilate in Period 1 will be attributed to dabigatran etexilate only.

Dose administration in Period 1 and in Period 2 will be separated by approximately 96 hours, with subjects remaining in the CRU.

In Period 2, on the morning of Day 5, a single oral dose of 60 mg quizartinib (two 30 mg tablets) will be given 2 hours prior to administration of a single oral 150 mg dabigatran etexilate (one 150 mg capsule) dose to subjects in the fasted state (after at least 10 hours fast) with approximately 240 mL of water. Subjects will continue to fast for at least 6 hours after dosing with quizartinib (4 hours after dosing with dabigatran etexilate).

Water should be restricted 1 hour before and 1 hour after dosing for each drug (eg, in Period 2, 1 hour before and 3 hours after dosing with quizartinib) and allowed ad libitum outside of this window. Subjects will follow a standardized meal schedule outside of the fasting window.

Serial blood samples for PK analysis in Period 2 will be taken relative to quizartinib dosing at: predose and 1, 2.5, 3, 3.5, 4, 5, 6, 8, 10, 14, 26, 38, 50, 62, and 74 hours postdose. The PK of dabigatran will be determined through 72 hours post-dabigatran dose, and the PK of quizartinib will be determined through 74 hours post quizartinib dose.

Safety evaluations (AEs, triplicate ECGs, clinical labs, concomitant medication, and vital signs) will be collected throughout the study period. ECGs recorded in triplicate will be recorded in Periods 1 and 2 (with 3 separate ECGs at least 2 minutes apart and the average of the 3 QTcF determinations used to determine safety parameters). On Day 1 of Period 1, triplicate ECGs will be recorded within 1 hour prior to dabigatran etexilate administration and at 2 and 6 hours after dabigatran etexilate administration. On Day 5, triplicate ECGs will be recorded within 1 hour prior to quizartinib administration and at 2, 4, and 8 hours after quizartinib administration.

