In clinical studies to date, the most common serious adverse reactions are myelosuppressive in nature and include infections, febrile neutropenia, and bleeding. Overall, the most common adverse reactions also included nausea, asthenic conditions, pyrexia, vomiting, and diarrhea. Further, there is a clear association between quizartinib and QT prolongation which occurs in a dose dependent manner. Risk management for QT prolongation in the multiple dose studies includes ECG (QTcF) based dose modifications (including dose escalation, dose interruption, dose reduction and dose discontinuation) as well as correction of electrolytes. In summary, the AEs observed with quizartinib treatment could be managed by monitoring, dose modifications,

and/or standard supportive therapies. Overall, quizartinib treatment was well tolerated at the proposed dose and dose regimen in adults with RR AML with FLT3-ITD. Furthermore, based on the results of the Transgenic Rat Mutation Assay (TGR) quizartinib is not mutagenic and can be dosed in healthy subjects (report ongoing).

Please refer to the most current version of the prescribing information for the risks associated with dabigatran etexilate and the most updated version of the Investigator's Brochure (IB) for the risks associated with quizartinib.

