5.2. Exclusion Criteria

Subjects who meet any of the following exclusion criteria within 21 days prior to Day -1 are not to be enrolled in this study.

Medical History

1. Any condition that may affect drug absorption, distribution, metabolism, and excretion.
2. History of clinically significant drug allergy.
3. Known hypersensitivity to quizartinib, dabigatran etexilate, or their excipients.
4. Major surgery within 90 days of Day -1.
5. History or presence of clinically significant cardiovascular disease, including any of the following:
 - Angina
 - TdP
 - Myocardial infarction
 - Coronary artery disease
 - Cardiomyopathy
 - Congestive heart failure
 - Cardiac valvular disease
 - Dysrhythmias
 - Cardiogenic syncope
 - Hypertension
 - Cerebrovascular accident
 - Transient ischemic attack
 - History of QT interval prolongation
 - Family history of QT interval prolongation
 - Diagnosed or suspected congenital long QT syndrome
6. History, or presence in the average of triplicate ECGs at Screening and Day -1, of any of the following cardiac conduction abnormalities:
 - QTcF >450 ms
 - Evidence of second- or third-degree atrioventricular block
 - Evidence of complete left or right bundle branch block

- QRS or T wave morphology that could, in the investigator's opinion, render QT interval assessment unreliable (confirmed with triplicate ECG)

7. History of any cancer, except non-melanoma skin cancer, or resected non-metastatic cancer with no evidence of disease accepted by the investigator and Sponsor medical monitor.
8. History or family history of bleeding disorders.
9. Presence of mechanical prosthetic heart valves.
10. Evidence of hepatitis B infection or hepatitis C antibody at Screening.
11. History or presence of human immunodeficiency virus (HIV) antibody.
12. Active infection within 30 days of Day -1.
13. Immunization within 30 days of Screening.
14. Inadequate venous access.

Medication Use and Lifestyle

15. Treatment with any investigational product in a clinical study within 30 days (or 5 drug half-lives, if 5 drug half-lives are expected to exceed 30 days) of Day -1.

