6.5. Guidelines for Dose Modification

Not applicable. No dose modification will be allowed.

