8.6.2.7.2. QTcF Prolongation, Torsades de Pointes, and Other Ventricular Arrhythmias

Subjects who experience >480 ms QTcF prolongation must be monitored closely with ECGs, performed twice weekly for the first week of the QTcF prolongation and then weekly thereafter until the QTcF prolongation is resolved. QTcF prolongation \geq Grade 3, either serious or non-serious and whether or not causally related, must be recorded as an AE or SAE in the eCRF within 24 hours of the assessment, with the investigator's assessment of seriousness, causality, and a detailed narrative.

Monitoring in subjects with QTcF prolongation will include the following:

- Electrolytes (potassium, calcium, and magnesium) should be checked and supplementation given to correct any values outside the normal range.
- Concomitant medications should be reviewed to identify and, if appropriate, discontinue any medication with known QT prolonging effects.

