9.4. Population for Analysis Sets

9.4.1. Pharmacokinetic Population

The PK analysis will be performed using the PK Population defined as all evaluable subjects who received at least 1 dose of study drug (quizartinib or dabigatran) and has a measurable concentration.

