9.5.1.3. Electrocardiograms

Results of triplicate ECGs and change from baseline will be summarized with descriptive statistics at each time point. The baseline value is defined as the last non-missing value before the initial administration of study drug. In addition, the number and percentage of subjects with ECG interval values meeting the criteria will be tabulated (eg, QTc \leq 450 ms, >450 to \leq 480 ms, >480 ms to \leq 500 ms, and >500 ms).

A listing of ECG data will be generated.

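### The 450 ms QTcF limit is last applied on Day -1: the Day 5 ECG taken just before quizartinib carries no stated dosing limit and is not the reference for ECG change after quizartinib

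*Combined protocol and SAP*

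**What the plan says.** Exclusion 6 (section 5.2) covers "History, or presence in the average of triplicate ECGs at Screening and Day -1, of any of the following cardiac conduction abnormalities", and the first item listed is QTcF above 450 ms. Section 4.1.1 places the last eligibility check on Day -1: "At CRU admission, eligibility will be reconfirmed and baseline safety evaluations, including ECGs recorded in triplicate will be assessed".

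Quizartinib is given once, on Day 5. Section 4.1.3 states "On Day 5, triplicate ECGs will be recorded within 1 hour prior to quizartinib administration", with further triplicates at 2, 4 and 8 hours. It also schedules Day 1 triplicates before dabigatran etexilate and at 2 and 6 hours after it. The mean of the three QTcF readings is the safety value.

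Section 6.5 reads "Not applicable. No dose modification will be allowed". Section 8.6.2.7.2 states "Subjects who experience >480 ms QTcF prolongation must be monitored closely with ECGs" and adds electrolyte and concomitant-drug checks.

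For the analysis, section 9.5.1.3 states "The baseline value is defined as the last non-missing value before the initial administration of study drug".

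**The concern.** Section 2.3 acknowledges a dose-dependent link between quizartinib and QT prolongation. It says of the wider programme: "Risk management for QT prolongation in the multiple dose studies includes ECG (QTcF) based dose modifications". With a single dose, the only comparable step is deciding whether to give it. The ECG that could inform the decision is already scheduled, but no value is attached to it. As written, a triplicate mean of 470 ms on Day 5 breaches no stated rule, although the same value on Day -1 would have excluded the subject. By contrast, inclusion 10 does set a condition tied to quizartinib dosing for low electrolytes.

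Subjects are healthy and expect no benefit (section 2.3). The dose cannot be taken back: section 2.1 gives effective half-lives of 73 hours for quizartinib and 119 hours for AC886.

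The second matter is the reference value. ECG change contributes to a secondary safety endpoint (section 3.2). If the reference is taken before Period 1, the change reported after quizartinib also contains whatever happened between Day 1 and Day 5.

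**Working it through.** The plan gives no figure of its own on this point. The first three steps are readings of the text. The rest uses assumed inputs and shows the range.

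**1. Timing.** Table 1.1 has no Day 0. Day -1 to Day 1 is 1 day and Day 1 to Day 5 is 4 days (about 96 hours, section 4.1.3), so 1 + 4 = 5 days. There is one Day 5 pre-dose triplicate per subject, at most 20 × 1 = 20 sets.

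**2. Is there a Day 5 dosing limit?**

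| Section | Content | Bars the Day 5 dose at a stated QTcF? |
|---|---|---|
| 5.2, exclusion 6 | >450 ms at Screening and Day -1 | No; earlier visits |
| 4.1.3, 8.6.6 | Day 5 pre-dose triplicate | No value given |
| 6.5 | No dose modification | No |
| 7.1 | General reasons, including AE and investigator decision | No value given |
| 8.6.2.1 | Investigator appraises all ECG results | Judgment only |
| 8.6.2.7.2 | >480 ms: monitoring; Grade 3 or higher: recorded as AE or SAE | No |

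**3. Which ECG is baseline?** Study drug covers both products (section 9.4.1, Table 6.1), and the first one given is dabigatran etexilate on Day 1. Baseline is therefore the Day 1 pre-dose ECG, or Day -1 if that is missing. Write B1 for this value, B5 for the Day 5 pre-dose value and Y for a value after quizartinib:

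mean(Y − B1) = mean(Y − B5) + mean(B5 − B1)

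The last term enters one for one. If it were 2 to 5 ms (an assumption), the reported mean change would move by 2 to 5 ms. The documents give neither size nor direction. Inclusion 9 asks for willingness to eat high-potassium foods for at least 24 hours before quizartinib, so conditions may differ between the two readings, but the Day 1 diet is not described.

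**4. How often would a 450 ms rule bite?** Assumed model: long-run QTcF is normal across subjects. Each triplicate mean adds normal within-subject error. Screening and Day -1 means are both at or below 450 ms. There is no drug effect. A share of 0%, 50% or 80% of the within-subject variance is common to the first and repeat Day 5 triplicates. Simulation used 4,000,000 subjects per setting.

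| Mean, between SD / within SD (ms) | First >450 | First and repeat >450 (0% / 50% / 80% shared) | Held subjects with long-run QTcF ≤450 (0% / 80% shared) |
|---|---|---|---|
| 400, 15/6 | 0.05% | 0.01% / 0.02% / 0.03% | 78% / 93% |
| 410, 15/8 | 0.47% | 0.08% / 0.17% / 0.28% | 81% / 92% |
| 410, 20/10 | 1.45% | 0.33% / 0.62% / 0.91% | 72% / 87% |
| 420, 20/10 | 3.03% | 0.78% / 1.37% / 1.97% | 68% / 83% |

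- Repeats needed: 20 × 0.0005 = 0.01 to 20 × 0.0303 = 0.6 subjects.
- Holds: 20 × 0.00009 = 0.002 to 20 × 0.0197 = 0.4 subjects.
- At least one hold: 1 − (1 − p)^20 = 0.2% to 33%.

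**5. What the repeat does**, at a fixed true QTcF with within SD 6 to 10 ms:

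| True QTcF | One triplicate >450 | Both >450 (0% to 80% shared) |
|---|---|---|
| 430 ms | 0.04% to 2.3% | at most 1.0% |
| 440 ms | 5% to 16% | 0.2% to 10% |
| 460 ms | 84% to 95% | 71% to 93% |

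The repeat cuts holds due to ordinary variation, and misses some subjects who are truly above the limit.

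**6. Cost to the PK comparison.** The 90% CI half-width on the log ratio is proportional to t(0.95, n−1)/√n: 0.3866 at n = 20, 0.3978 at 19 and 0.4100 at 18. The ratios to n = 20 are 1.029 and 1.060.

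**7. Does a repeat fit?** Section 4.1.3 allows 1 hour before dose; Table 10.4 allows 30 minutes. With 5 minutes of rest and two gaps of 2 to 3 minutes, two triplicates take 2 × (5 + 4) = 18 to 2 × (5 + 6) = 22 minutes. If the 5 additional minutes in Table 10.4 are used each time, they take 2 × (10 + 6) = 32 minutes, before any reading time. A repeat fits the 1-hour window but is not shown to fit the 30-minute one.

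**The case against.** **Existing protection.** QTcF is watched between Day -1 and Day 5: there are three triplicates on Day 1, and the investigator must appraise every ECG. Grade 3 or higher prolongation must be recorded as an AE or SAE, and AE is a listed reason for discontinuation. Subjects stay in the unit, and other medicines are restricted. QT history, family history and QT-prolonging drugs are excluded, and section 4.2 reports that single doses up to 90 mg were well tolerated. This stands and limits the risk, but it leaves the decision without a stated value.

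**The choice of 450 ms.** It is an entry limit, whereas the in-study action level is above 480 ms, and most held subjects would be within the limit in the long run. The second half stands as a real cost. On the first, the Day 5 decision is whether to expose a subject to quizartinib for the first time, which is the decision the entry limit serves; the 480 ms level triggers monitoring.

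**The multiple-dose comparison.** Those rules adjust repeated dosing, so the analogy is loose. It shows that the sponsor uses QTcF to manage this risk, not that a particular rule is owed here.

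**The baseline.** A drug-free Day 1 value is defensible, laboratory tests and vital signs use the same definition (9.5.1.2, 9.5.1.4), and section 9.5 announces a separate SAP that could define a period-specific reference. This argues for also showing change from Day 1. It does not make Day 1 the better reference for change after quizartinib, and a SAP would not normally set a dosing limit.

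**Conclusion.** Both parts hold in a limited form. The numerical QTcF limit is last applied five days before quizartinib, and the pre-quizartinib triplicate has no stated value at which the dose is withheld. Under the protocol's definition, that same triplicate is a post-baseline value. Correcting both is worthwhile and cheap, though neither has a demonstrated effect on results.

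A reader might infer more than the documents support:

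- That a subject with a long QTcF must be dosed. Section 6.5 concerns dose modification and does not forbid withholding; sections 7.1 and 8.6.2.1 leave that to the investigator.
- That the reported change after quizartinib is biased by some milliseconds. The 2 to 5 ms figure is an illustration only. The Day 5 pre-dose values are still summarised and listed.
- That other results are compromised. The QTc categories in 9.5.1.3 are absolute values, and PK does not depend on the ECG baseline.
- That the expected holds measure toxicity. They describe ordinary variation under assumed means of 400 to 420 ms, between-subject SDs of 15 to 20 ms and within-subject SDs of 6 to 10 ms. The documents give no frequency of readings above 450 ms.

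On those assumptions, fewer than one hold is expected in 20 subjects, and 68% to 93% of held subjects would have a long-run QTcF at or below 450 ms.

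**What to change.** 1. **Dosing rule, sections 4.1.3 and 7.1.** Require the investigator to read the Day 5 pre-dose triplicate mean QTcF before quizartinib is given. If it exceeds 450 ms, repeat the triplicate once. If the repeat mean also exceeds 450 ms, withhold both Day 5 doses and do the early-termination assessments. Start the first triplicate early in the 1-hour window and bring the 30-minute limit in Table 10.4 into line with it. With 32 minutes for two triplicates, 60 − 32 = 28 minutes remain for reading and the other pre-dose procedures.

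2. **Reference value, section 9.5.1.3.** Report ECG change after quizartinib from the Day 5 pre-dose value, and keep the Day 1 baseline for Period 1. Change from Day 1 can be shown alongside, which keeps the ECG tables comparable with the laboratory and vital-sign tables.

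The cost is a few sentences in an amendment and a repeat triplicate in an expected 0.01 to 0.6 of 20 subjects; the second change needs no new data. The downside is that a held subject gives no test-period data, and replacement needs sponsor approval (section 5.4). One lost pair widens the 90% CI on the log ratio by about 3%, two by about 6%.

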4.1.4. Duration

Anticipated total duration of the study, excluding screening, is approximately 12 days. The study overall will be completed when the last datapoints for primary and secondary endpoints are collected and recorded.

4.2. Justification for Dose

In this study, subjects will be given quizartinib as two 30 mg tablets (60 mg total dose) under fasted conditions. This is the highest proposed clinical dose of quizartinib which is being investigated in the first line treatment for AML (QuANTUM-First study) and the highest clinical dose approved in Japan for the treatment of adult patients with relapsed/refractory FTL3-ITD-positive AML. Single doses of up to 90 mg have been administered to healthy subjects in a prior study (AC220-014) and are well tolerated.

The highest approved clinical dose of dabigatran etexilate is 150 mg. Therefore, the effect of quizartinib on dabigatran etexilate will be assessed at a dose of 150 mg.

5. STUDY POPULATION

This Phase 1 study is being conducted in healthy subjects.

5.1. Inclusion Criteria

Subjects eligible for inclusion in this study have to meet all inclusion criteria for this study.

1. Voluntarily consents to participate in this study and provides written informed consent before the start of any study-specific procedures.
2. Male and female subjects 18 to 55 years of age, (inclusive), with a body mass index (BMI) of 18 kg/m² to 32 kg/m², inclusive, at Screening.
3. In females, documented surgical sterilization, postmenopausal status for at least 1 year (follicle stimulating hormone [FSH] >40 mIU/mL serum at Screening), or agreement to have sterile male partner, or agreement to use 1 of the protocol-approved means of contraception from Screening until 6 months after the dose of quizartinib. See Section 5.3 Contraception Requirements.
4. In males, documented surgical sterilization, or sexual abstinence, or agreement to use 1 of the protocol-approved means of contraception from Screening until 6 months after the dose of quizartinib. See Section 5.3 Contraception Requirements.
5. In females, must not retrieve eggs/ova via assisted reproductive technology (ART) either for their own use or donation while on study or for 6 months after the last dose of quizartinib, whichever is later.
6. In males, agreement to avoid sperm donation for 6 months after the dose of quizartinib.
7. Determined to be healthy by the investigator based on medical history, medical examination, vital signs, and 12-lead ECG during Screening and through Day -1.
8. Clinical laboratory findings are within normal range or if outside the normal range, deemed not clinically significant in the opinion of the investigator and the Sponsor medical monitor during Screening and on Day -1 Serum creatinine $\leq 1.5 \times$ ULN and estimated creatinine clearance (CrCl) ≥ 80 mL/min according to the Cockcroft-Gault equation, at Screening and on Day -1.
9. Willingness to consume high-potassium foods, such as bananas, cantaloupe, oranges (excluding blood orange), orange juice (excluding blood orange juice), and yogurt, for at least 24 hours before quizartinib administration on Day 5 (except during the fasting period).
10. Serum potassium, magnesium, and calcium (corrected for albumin level) within normal limits. Subjects with values below normal at Screening or on Day -1 may be eligible if levels of these electrolytes were corrected before quizartinib administration.
11. Serum TBil, ALT, and aspartate aminotransferase (AST) not above ULN at Screening or on Day -1. Values above the ULN may be acceptable if not clinically significant, with the Sponsor's agreement.

12. Hemoglobin, platelets, and absolute neutrophil count within normal limits at Screening or on Day -1. Hemoglobin below the lower limit of normal may be acceptable if not clinically significant, with the Sponsor's agreement.

